## 11.2 Clinical Laboratory Variables

Clinical laboratory data (biochemistry, haematology, and biochemical bone markers) will be summarised by parameter and visit for Part 1 for the Safety Analysis Set 1 (**Tables 4.6.1.1, 4.6.1.2 and 4.6.1.3**, respectively).

Clinical laboratory data (biochemistry, haematology, and biochemical bone markers) will be summarised by parameter, visit and treatment group for Part 2 and 3 for the Safety Analysis Set 2 (**Tables 4.6.2.1, 4.6.2.2 and 4.6.2.3**, respectively). Additionally, summarization will also be performed by parameter and visit for Lanthanum Carbonate for Parts 2 and 3 for the SCS (**Tables 4.6.2.4, 4.6.2.5 and 4.6.2.6**, respectively).

Descriptive statistics (n, mean, standard deviation, minimum, median, and maximum) for clinical laboratory values (in SI units) and changes from baseline at each assessment time point as well as shift tables (in terms of abnormality: low, normal, and high) from baseline to each visit for quantitative variables will be presented for the following clinical laboratory variables for Part 2 and 3 for the Safety Analysis Set 2 (**Tables 4.6.3.1, 4.6.3.2, 4.6.3.3**) and SCS (**Tables 4.6.3.4, 4.6.3.5 and 4.6.3.6**).

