**Table 3: Schedule of Assessments for Part 2b and Part 3**

	Part 2b (Visit window ±3 days)				Part 3 (Visit window ±1 week)		
Visit	1.0a	Washout W1b	2.1-2.3	2.4	3.0-3.4	3.5/End of Studyc	Safety Follow-up callj
Week	0	0-3 weeks duration	2, 4, 6d	8d	12, 16, 20, 24, 28	32d	33-34d

d Visit weeks may be variable depending on duration of washout (+3 weeks).

e Local laboratory assessments for phosphorus in Part 2b are for titration purposes, as required, and will not be analyzed; data from Visits 3.0-3.4 will be collected and assessed.

f Visit 2.2 only; Each subject will have at least 2 samples taken for pharmacokinetic assessment. These should be taken during defined time windows (to be selected from: 0-2 hours, 2-4 hours and 4-6 hours, after the first dose/meal of the day). Note: If the sampling is not done at Visit 2.2, blood sampling for pharmacokinetics must be taken at an alternative visit during Part 2b.

g Visit 3.3 only; Each subject will have at least 2 samples taken for pharmacokinetic assessment. These should be taken during defined time windows (to be selected from: 0-2 hours, 2-4 hours and 4-6 hours, after the first dose/meal of the day). Note: If the sampling is not done at Visit 3.3, blood sampling for pharmacokinetics must be taken at an alternative visit during Part 3.

h Investigational product will be dispensed at Visit 1.0 if eligible, however if a washout is required then investigational product will be dispensed at visit W1.

i For subjects entering Part 3 only.

j Safety follow-up call to be made 7-14 days following last dose of investigational product. For subjects discontinued due to kidney transplantation, the safety follow up call to be made 30 ± 7 days from the last dose.

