**7.1.2.5 Part 2a: Visits 2.5-2.7 (Weeks 10, 12, and 14, Nominally;  $\pm 3$  Days)**

- Subjects will attend the clinic every 2 weeks for scheduled study visits.
- At Visit 2.6 only, blood samples will be taken to measure lanthanum pharmacokinetics (2 samples to be selected from: 0-2 hours, 2-4 hours, or 4-6 hours). **Note:** If the sampling is not done at Visit 2.6, blood sampling for pharmacokinetics must be taken at an alternative visit during Part 2.
- Phosphate levels will be measured locally at Visits 2.5, 2.6 and 2.7 only, for titration purposes.
- The investigational product dispensed at the previous visit will be counted, compliance calculated and the container returned to the subject until exhausted. If necessary, a new container of investigational product will be dispensed.
- The dose of lanthanum carbonate will be adjusted and dispensed as required.
- Any AEs that occurred since the last visit will be recorded.
- A review of any concomitant medication taken since the last visit will be undertaken and changes recorded.
- Confirmation of dialysis adequacy and dietary advice will be made.

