**7.1.2.7 Part 2b: Visits 2.1-2.3 (Weeks 2, 4, and 6; Nominally;  $\pm 3$  Days)**

- Subjects will attend the clinic every 2 weeks for scheduled study visits, starting from the first dose of investigational product.
- At Visit 2.2 only, blood samples will be taken to measure lanthanum pharmacokinetics (2 samples to be selected from: 0-2 hours, 2-4 hours, or 4-6 hours). **Note:** If the sampling is not done at Visit 2.2, blood sampling for pharmacokinetics must be taken at an alternative visit during Part 2b.

- Phosphate levels will be measured locally at Visits 2.1, 2.2 and 2.3 only, for titration purposes.
- The investigational product dispensed at the previous visit will be counted, compliance calculated and the container returned to the subject until exhausted. If necessary, a new container of investigational product will be dispensed.
- The dose of lanthanum carbonate will be adjusted and dispensed as required.
- Any AEs that occurred since the last visit will be recorded.
- A review of any concomitant medication taken since the last visit will be undertaken and changes recorded.
- Confirmation of dialysis adequacy and dietary advice will be made.

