**7.1.2.8 Part 2b: Final Visit (Visit 2.4; Week 8; Nominally;  $\pm 3$  Days)**

- A 12-lead ECG will be performed.
- Vital signs, height and weight will be measured.
- Blood samples will be taken for biochemistry, and biochemical bone markers.
- Any unused lanthanum carbonate will be collected and drug accountability performed.
- Any AEs that occurred since the last visit will be recorded.
- A review of any concomitant medication taken since the last visit will be performed and changes recorded.
- Confirmation of dialysis adequacy and dietary advice will be made.
- For subjects entering Part 3, lanthanum carbonate will be dispensed at a dose determined by the Investigator based on serum phosphorus levels taken at each study visit up to a maximum dose of 3000mg/day.

**7.1.2.9 Part 3 (Visits 3.0-3.4: Weeks 20, 24, 28, 32, and 36;  $\pm 1$  Week for Part 2a; Weeks 12, 16, 20, 24, and 28 for Part 2b)**

- Subjects who have successfully completed Part 2 of the study will continue to be dispensed lanthanum carbonate for a further 6 months.
- Subjects will attend the clinic once every month for scheduled study visits.
- At Visits 3.0-3.4 the local lab results for serum calcium, serum phosphorus, and calcium phosphorus product will be taken for analysis.
- At Visit 3.3 only, blood samples will be taken to measure lanthanum pharmacokinetics (2 samples to be selected from: pre dose to 2 hours, 2-4 hours, and 4-6 hours). **Note:** If the sampling is not done at Visit 3.3, blood sampling for pharmacokinetics must be taken at an alternative visit during Part 3.
- The dose of lanthanum carbonate will be adjusted and dispensed as required and any unused lanthanum carbonate will be collected, and drug accountability performed.
- Any AEs that occurred since the last visit will be recorded.

- A review of any concomitant medication taken since the last visit will be undertaken and changes recorded.
- Confirmation of dialysis adequacy and dietary advice will be made.

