## 9.11 Safety Analyses

All safety variables will be summarized using the defined Safety Analysis Sets (Safety Analysis Set 1, Safety Analysis Set 2, and SCS; see Section 9.5). Summaries will be presented by treatment group and overall.

Adverse events will be coded using the Medical Dictionary for Regulatory Activities, Version 13.0.

The number of events, incidence, and percentage of treatment-emergent adverse events (TEAEs) will be calculated overall, by system organ class, and by preferred term. Treatment-emergent AEs will be further summarized by age group, severity and relationship to investigational product. Adverse events related to investigational product, AEs leading to withdrawal, SAEs, and deaths will be summarized/listed. Clinical laboratory tests, vital signs, and ECG findings will be summarized. Potentially clinically important findings will also be summarized or listed.

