## APPENDIX 2 GUIDELINES FOR PHOSPHORUS AND CALCIUM

The following guidelines summarize the requirements for each parameter during the study.

Parameter	Value	Age Range (Years)	Action
Phosphate	<4.0mg/dL (1.29mmol/L)	12 to <18	Monitor phosphate levels carefully and consider reducing the binder dose by 25% depending on the rate at which phosphate is falling.
	<4.5mg/dL (1.45mmol/L)	10 to <12	
Phosphate	<3.5mg/dL (1.13mmol/L)	12 to <18	Binder should be stopped and phosphate levels monitored closely. The binder should be resumed at 50% of the prior dose when phosphate levels are >4.0mg/dL (1.29mmol/L).
Phosphate	<4.0mg/dL (1.29mmol/L)	10 to <12	Binder should be stopped and phosphate levels monitored closely. The binder should be resumed at 50% of the prior dose when phosphate levels are >4.5mg/dL (1.45mmol/L).
Phosphate	>10.0mg/dL (3.23mmol/L) except during washout periods	10 to <18	Discontinue subject.
Calcium	<8.8mg/dL (2.20mmol/L)	10 to <18	Subject should receive therapy to increase calcium levels.
Calcium	>10.2mg/dL (2.54mmol/L) during Part 2 Treatment Period 1	10 to <18	Active vitamin D sterols should be decreased by 50%, calcium carbonate decreased by 25% and the subjects should be monitored. If after 2 weeks hypercalcaemia persists, active vitamin D sterols should be stopped. If after another 2 weeks it persists the subject should be withdrawn from Part 2 and may continue to Part 3.
Calcium	>10.2mg/dL	10 to <18	Active vitamin D sterols

Parameter	Value	Age Range (Years)	Action
	(2.54mmol/L) during lanthanum carbonate treatment		should be decreased by 50%, calcium carbonate decreased by 25% and the subjects should be monitored. If after 2 weeks hypercalcaemia persists, active vitamin D sterols should be stopped.
Calcium	>11.5mg/dL (2.88mmol/L) during first treatment period of Part 2	10 to <18	Discontinue subject from Part 2, and proceed to Part 3.

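### The SAP omits, without declaring it, the protocol's report of potentially clinically important findings, and three of four on-treatment phosphate values per lanthanum period reach no laboratory safety table

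*SAP*

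**What the plan says.** - **Commitment.** Protocol 9.11, after naming laboratory tests, vital signs and ECG, adds: "Potentially clinically important findings will also be summarized or listed". The synopsis repeats this.
- **Planned laboratory outputs.** SAP 11.2: "Clinical laboratory data (biochemistry, haematology, and biochemical bone markers) will be summarised by parameter, visit and treatment group for Part 2 and 3". It adds "shift tables (in terms of abnormality: low, normal, and high) from baseline to each visit". Listing 8.1.2 covers all laboratory results; no criteria or flags are described, and the SAP does not say whether local titration values are in it.
- **Declared changes.** SAP 17 lists several departures from the protocol. None concerns potentially clinically important findings.
- **Source of phosphate values.** Part 2b (Protocol 7.1.2.7): "Phosphate levels will be measured locally at Visits 2.1, 2.2 and 2.3 only, for titration purposes". Part 2a, lanthanum period (Protocol 7.1.2.5): "Phosphate levels will be measured locally at Visits 2.5, 2.6 and 2.7 only, for titration purposes". At the Part 2b Week 8 visit (Protocol 7.1.2.8): "Blood samples will be taken for biochemistry, and biochemical bone markers". Visit 2.8 in Part 2a has the same panel.
- **Status of local values.** Protocol Table 3, footnote e: "Local laboratory assessments for phosphorus in Part 2b are for titration purposes, as required, and will not be analyzed". SAP 10.3 repeats the rule for Parts 1 and 2, then allows local values where central ones are missing.
- **Low phosphate.** Protocol Appendix 2 gives age-specific limits. Below the lower one (3.5 mg/dL at 12 to <18 years, 4.0 mg/dL at 10 to <12 years) it says: "Binder should be stopped and phosphate levels monitored closely".
- **Use of interruptions.** SAP 4.6 and 21.1 treat subjects interrupted for hypophosphatemia as meeting the 8-week treatment requirement. No output counts them.

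**The concern.** Protocol 9.13 and SAP 2.5 say the study was refocused on safety. Interrupting the binder for low phosphate is an event that the protocol itself anticipates for the drug under test, and the dose is titrated at exactly the visits whose phosphate values are local. If the safety tables see phosphate only at Week 8, they see it after any correction has been made. A reader of the study report could then take the Week 8 shift table as the frequency of low phosphate on treatment, when it describes one visit out of four. The protocol's separate promise to report important findings would have caught this, but it has no counterpart in the SAP.

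**Working it through.** **1. Protocol against SAP.** Protocol 9.11 requires a summary or a listing. SAP 11.2 to 11.4 and the output list in SAP 20 contain no criterion for potentially clinically important laboratory values, and no table or flagged listing of them. SAP 17 is silent. The omission is therefore both real and undeclared.

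**2. Which phosphate values reach a laboratory safety table.**

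| Lanthanum period | Weeks 2, 4, 6 of the period | Week 8 of the period |
|---|---|---|
| Part 2b | Visits 2.1, 2.2, 2.3: local | Visit 2.4: biochemistry panel |
| Part 2a, Period 2 | Visits 2.5, 2.6, 2.7: local | Visit 2.8: biochemistry panel |

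Not tabulated for safety: 3 / (3 + 1) = 3 of 4 in each lanthanum period. The calcium carbonate period has the same layout (Visits 2.1-2.3 local, Visit 2.4 panel), so Part 2a as a whole gives 6 of 8. This count needs no assumption.

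**3. Following one subject.** A phosphate value below the lower Appendix 2 limit at Week 4 of lanthanum stops the binder temporarily, and the value has recovered by Week 8.
- Laboratory tables: only the recovered Week 8 value appears.
- Shift tables: these class values as low, normal or high, not against the Appendix 2 limits.
- Exposure and compliance tables (SAP 8): they do not count interruptions.
- Adverse events of special interest (SAP 11.1): bone events only.
- Visit 3.5 panel: triggered by withdrawal from the study, not by a temporary stop.
- Adverse event tables: the event appears if it is reported.
- By-week efficacy tables (SAP 10.3): the value may appear, depending on how the missing-central rule is applied.

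**4. Possible size of the undercount.** The documents give no rate of low phosphate, so what follows is assumption. Let p be the risk of being below a limit at any one visit, equal at all four visits. Suppose a Week 8 table did use the Appendix 2 limits; it would show p. The share of subjects ever below the limit then satisfies p ≤ P(ever) ≤ 4p.
- Full within-subject correlation: P(ever) = p, so no undercount.
- Independence: P(ever) = 1 − (1 − p)^4.
  - p = 1%: 3.9%, ratio 3.9
  - p = 3%: 11.5%, ratio 3.8
  - p = 5%: 18.5%, ratio 3.7

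**5. The plan's own safety figure.** SAP 2.5 gives an 80.6% chance of observing at least one event among 32 subjects at a true rate of 5%. Check: 1 − 0.95^32 = 0.806, which reproduces. The calculation supposes that every event is seen. If only a fraction f of affected subjects have the event in a tabulated sample, the chance is 1 − (1 − 0.05f)^32: 80.6% at f = 1, 70.6% at 0.75, 55.5% at 0.5 and 33.1% at 0.25. The documents do not give f, and adverse event reports would raise it.

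**The case against.** The strongest reply has five parts.

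- **A listing exists.** The protocol promised a summary or a listing, and Listing 8.1.2 lists all laboratory data. ECG shifts in SAP 11.4 do separate out clinically significant abnormality, and SAP 1 puts table and listing specifications in a separate document, where flags might be defined. This narrows the point: reporting of important findings is not dropped altogether. It does not answer it, because an unflagged listing without criteria does not identify important findings, and the SAP neither sets criteria nor says that local values are included.
- **Local values are not wholly excluded.** A reader might infer that Part 2 local values are left out of every analysis. The documents do not support that. SAP 10.1, 10.3 and 21.1 use them when central data are missing, and Table 3 schedules a local test at Visit 1.0 that could serve as baseline. They may therefore enter the by-week efficacy tables. Nothing brings them into the safety tables.
- **Adverse event reporting is not purely discretionary.** Protocol 8.1.5 gives criteria, including a shift from normal to abnormal during treatment. This stands, but the same section leaves the decision on clinical significance to the investigator.
- **A 4-fold undercount is not established.** It is tempting to state this as the result. It is about the ceiling under equal per-visit risk. Equal risk is itself doubtful, since subjects start above target and the dose is titrated every two weeks. The planned shift table also does not use the Appendix 2 limits, so it would not show p.
- **A wider table could mislead.** Local calcium is specified at the calcium carbonate titration visits (Protocol 7.1.2.2) but not in the text for the lanthanum visits (7.1.2.5, 7.1.2.7). A by-treatment count of any abnormal calcium value would be unequal by design. Mixing in unscheduled values would count more events in subjects tested more often. Both points are accepted and shape the fix.

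**Conclusion.** The point holds in this form. The SAP plans no table or flagged listing of potentially clinically important findings and does not declare that departure in Section 17. Its laboratory safety tables leave out 3 of the 4 scheduled on-treatment phosphate values in each 8-week lanthanum period. A low value that recovers by Week 8 after a temporary binder stop reaches a summary table only as a reported adverse event, or possibly in an efficacy table by week.

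The 3-of-4 count is firm. The effect on the reported frequency is not: with equal per-visit risk it ranges from none to about 4-fold, and the documents do not say where in that range it lies. A reader might also infer that low phosphate removes a subject from the study. It does not: Protocol 6.2.1 and Appendix 2 describe a stop with resumption, and low phosphate is not among the subject stopping criteria in Protocol 4.4.1. No sample size or power figure changes.

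**What to change.** 1. **SAP 11.2, one table.** By treatment, give the number of subjects with any scheduled on-treatment phosphate value, local or central, below each age-specific limit already in protocol Appendix 2, with the number of subjects tested as denominator. Show unscheduled values separately.
2. **One listing.** List binder interruptions for hypophosphatemia with the triggering value. SAP 4.6 and 21.1 already need these subjects to be identified.
3. **Local values.** Limit the rule that Part 2 local values are not analysed to the efficacy summaries, and say whether Listing 8.1.2 contains them.
4. **SAP 17.** Record the change.
5. **Calcium.** Do not add a by-treatment table of any abnormal calcium value; report calcium from the scheduled central panel.

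The cost is a small amount of programming and confirmation that the Part 2 local phosphate values are in the database. SAP 21.1 draws on local values only for baseline and Week 8, so the Week 2, 4 and 6 values need checking. If they were not captured, retrieving them from sites (up to 36 are planned) would cost more, and SAP 17 should at least state the limitation.

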### Biochemistry

Blood samples (approximately 4.0mL) for biochemistry will be taken according to the Schedule of Assessments (see [Table 1](#) and [Table 3](#)). The following parameters will be assessed:

Sodium	Alanine aminotransferase (ALT)
Potassium	ALP
Calcium	Gamma glutamyl transferase (GGT)
Urea	Total bilirubin
Creatinine	Magnesium
Albumin	Serum phosphorus
Total protein	25-hydroxy Vitamin D a
Aspartate aminotransferase (AST)	

a 25-hydroxy Vitamin D will be measured at baseline and End of Study (EOS) only.

### Haematology

Blood samples (approximately 500µL) for haematology will be taken according to the Schedule of Assessments (see [Table 1](#) and [Table 3](#)). The following parameters will be assessed:

Haemoglobin	Mean corpuscular haemoglobin (MCH)
Haematocrit	Mean corpuscular haemoglobin concentration (MCHC)
Red blood cells	White blood cell count – total and differential
Mean corpuscular volume (MCV)	Platelet count

### Biochemical Bone Markers

Blood samples (approximately 3.0mL) for biochemical bone markers will be taken according to the Schedule of Assessments (see [Table 1](#) and [Table 3](#)). The following parameters will be assessed:

Tartrate-resistant acid phosphatase	Bone ALP
Osteocalcin	Sclerostin
Fetuin- A	PTH
FGF-23	

Normal ranges for all clinical laboratory data parameters (biochemistry, haematology, and biochemical bone markers) will be listed (**Tables 4.6.5.1, 4.6.5.2 and 4.6.5.3**, respectively). All clinical laboratory data including serum pregnancy test results will be listed (**Listings 8.1.1** [clinical laboratory sample collection and results for pregnancy] **and Listing 8.1.2** [clinical laboratory test results]).

### 11.3 Vital Signs

Vital signs data [height (cm), weight (kg), pulse (beats/min), systolic blood pressure (mmHg), and diastolic blood pressure (mmHg)] will be summarised by visit and by timepoint (for Visit 1.1); by Lanthanum Carbonate for Part 1 (**Table 4.7.1**), by treatment group for Part 2 and 3, for Lanthanum Carbonate only for Part 2 and 3 for the Safety Analysis Set 2 (**Table 4.7.2 and Table 4.7.3**, respectively) and for Lanthanum Carbonate only for Part 2 and 3 for the SCS (**Table 4.7.4**). Baseline is defined as the last assessment prior to the first dose of IP. A detailed description of Baseline, for the study, for treatment groups in Parts 2 and 3, can be found in the TLG shells, Appendix 2.

Descriptive statistics (n, mean, standard deviation, minimum, median, and maximum) for vital sign variables and their changes from baseline at each post-baseline visit will be presented.

All vital signs data will be listed (**Listing 8.2.1**).

### 11.4 Electrocardiogram (ECG)

ECG interpretation will be summarised by visit for Lanthanum Carbonate only for Parts 2a and 3 combined and Parts 2b and 3 combined for the Safety Analysis Set 2 (**Table 4.8.1 and Table 4.8.2**, respectively) and the SCS (**Table 4.8.3 and Table 4.8.4**, respectively). A shift table (in terms of clinical significance: normal, abnormal not clinically significant, and abnormal clinically significant) from baseline to each visit for qualitative ECG results will be presented for Lanthanum Carbonate only for Parts 2a and 3 combined and Parts 2b and 3 combined for the Safety Analysis Set 2 (**Table 4.8.5 and Table 4.8.6**, respectively) and for the SCS (**Table 4.8.7 and Table 4.8.8**, respectively).

ECG Investigator interpretations will be listed (**Listing 8.3.1**).

### **11.5 Other Safety Variables**

No other safety assessments/variables are planned for this study.

## **12. CLINICAL PHARMACOKINETIC AND PHARMACODYNAMIC ANALYSES**

### **12.1 Pharmacokinetics Population (and Pharmacodynamic Population, if applicable)**

**Pharmacokinetic Set 1** - Subjects in the Safety Analysis Set 1 who have at least 1 measurable post-dose plasma concentration of Lanthanum Carbonate. Subjects in Part 1 who vomited may be excluded from Pharmacokinetic Set 1.

**Pharmacokinetic Set 2** - Subjects in Safety Analysis Sets 1 or 2 who have at least 1 measurable post-dose plasma concentration of Lanthanum Carbonate will be included in Pharmacokinetic Set 2.

### **12.2 Pharmacokinetic Methods**

#### **12.2.1 Concentration Data**

Plasma lanthanum concentrations will be measured using Inductively Coupled Plasma Mass Spectrometry.

